5.2. Participant Dispositions

The number of participants in the following disposition categories will be summarized throughout the study by intervention group and overall:

- Participants randomized
- Participants who received study intervention
- Participants who completed, discontinued study intervention and reasons for discontinuation
- Participants who completed, terminated study prematurely and reasons for termination

Listings of participants will be provided for the following categories:

- Participants who discontinued study intervention
- Participants who terminated study prematurely (trial disposition page)
- Participants who were unblinded during the study period
- Participants who were randomized yet did not receive study intervention.

These summaries and listings will be provided for the randomized analysis set.

5.3. Primary Endpoint(s) Analysis

The primary endpoint analysis will be based on the full analysis set using the MADRS total scores collected during the double-blind treatment phase.

5.3.1. Definition

The MADRS is a clinician-administered scale designed to measure depression severity and detects changes due to antidepressant intervention (Montgomery 1979). The scale consists of 10 items, each of which is scored from 0 (item not present or normal) to 6 (severe or continuous presence of the symptoms). Higher scores represent a more severe condition. The MADRS evaluates reported sadness, apparent sadness, inner tension, reduced sleep, reduced appetite, concentration difficulties, lassitude, inability to feel, pessimistic thoughts, and suicidal thoughts. The test exhibits high inter-rater reliability. The recall period for the MADRS is 7 days.

The MADRS total score is the sum of scores from individual question items at a given time point and ranges from 0 to 60. Higher scores represent a more severe condition. Imputation of the total score is presented in section 5.1.3.

Negative changes in the MADRS total score indicate improvement.

5.3.2. Estimand

Primary Trial Objective: To evaluate the efficacy of JNJ-55308942 compared to placebo on symptoms of depression in participants with BD in an MDE

Estimand Scientific Question of Interest: What is the effect of assigning BD patients in an MDE to JNJ-55308942 vs. placebo in reducing the symptoms of depression after 6 weeks of treatment if no participant discontinued the treatment?

The estimand for the primary efficacy analysis is defined by the following 5 components:

Study Intervention: JNJ-55308942 mg once daily versus placebo

Population: participants with BD types I and II and in an MDE

Variable: change from baseline in the MADRS total score to Week 6

Population-level Summary: the difference in mean change from baseline in MADRS total score to Week 6 between JNJ-55308942 mg once daily and placebo

Intercurrent events and their corresponding strategies:

	Strategy for Addressing Intercurrent Events and
Intercurrent Events	Its Description
Discontinuation of study intervention	Hypothetical strategy: as if no participant
-	discontinued the study intervention. After study
	intervention discontinuation, similar efficacy is
	assumed for participants who discontinued as those

 $CONFIDENTIAL-FOIA\ Exemptions\ Apply\ in\ U.S.$

Intercurrent Events	Strategy for Addressing Intercurrent Events and Its Description
	participants from the same intervention group who
	did not discontinue the study intervention.
Change or discontinuation of	Hypothetical strategy: same as above. Change or
background therapy (mood stabilizer	discontinuation of background therapy will result in
and/or antipsychotic)	discontinuation of study intervention.

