6.7. Concomitant Therapy

All prestudy therapies administered up to 4 weeks before the intial screening visit must be recorded at screening.

Any administration of concomitant therapy throughout the study, from signing of the screening informed consent to final follow-up visit, must be recorded in the eCRF.

All therapies (prescription or over-the-counter medications, including vaccines, vitamins, herbal supplements; non-pharmacologic therapies such as electrical stimulation, acupuncture, special diets, exercise regimens, or other specific categories of interest) different from the study intervention must be recorded in the eCRF. Recorded information will include a description of the type of therapy, duration of use, dosing regimen, route of administration, and indication.

One of the following regimens will be followed for the concomitant medication status:

- Participants who are currently unmedicated and have not received any mood stabilizers or antipsychotics for four weeks before screening.
- Participants who are on a stable monotherapy regimen of one of the following mood stabilizers (lithium, valproate forms [e.g., divalproex sodium], or lamotrigine) or one of the following antipsychotics (lurasidone, cariprazine, quetiapine, lumateperone, or olanzapine) for four weeks before screening.
- Participants who are on a stable adjunctive regimen of one of the following antipsychotics (lurasidone, quetiapine, lumateperone, or olanzapine) and one of the following mood stabilizers (lithium, or valproate forms [e.g., divalproex sodium]) may be considered for eligibility based on the approved therapies in each market with an eligibility assessment conducted between the investigator and sponsor. Assessment of the stable adjunctive regimen of an antipsychotic and a mood stabilizer will be conducted by the investigator and sponsor's clinical judgement and documented for each participants. This regimen must be in place 4 weeks before screening.

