Participants will continue to take their current medication regimen, if applicable, throughout the study at an adequate and tolerated dose. No dose changes are permitted from screening through the end of the study (until after the follow-up visit). Modification of an effective pre-existing therapy should not be made for the explicit purpose of entering a participant into the study. Newly initiated psychotherapy (defined as psychotherapy that was started within 4 weeks of the screening visit) is prohibited. Regular ongoing psychotherapy that was initiated prior to 4 weeks before the screening visit will be permitted.

JNJ-55308942 is a weak inducer of CYP~~CCI~~, and a moderate inhibitor of CYP~~CCI~~. It is preferred that the use of co-medications that are metabolized solely by CYP~~CCI~~ is avoided, or participants should be carefully monitored.

JNJ-55308942 is mainly metabolized by CYP~~CCI~~ Therefore, co-administration with moderate or strong inhibitors/inducers of CYP~~CC~~ should be avoided.

See section [10.6](#), (Appendix 6: Disallowed Concomitant Therapies) for an important list of prohibited concomitant medications from 4 weeks prior to the screening visit until 7 days after last dose of study intervention. Of special note, treatment with antidepressants is not allowed in the study.

Following any administration of any disallowed concomitant medication during the study, the sponsor and investigator will evaluate whether a participant should be discontinued or remain in the study.

The sponsor must be notified in advance (or as soon as possible thereafter) of any instances in which prohibited therapies are administered.

See Section [10.6](#) for more information on disallowed concomitant therapies.

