7.2. Discontinuation of Study Intervention

A participant's study intervention must be discontinued if:

- Serious violation of protocol procedures after discussion with and agreement of the medical monitor
- The participant withdraws consent to receive study intervention
- The investigator or sponsor believes that for safety reasons or tolerability reasons (e.g., an SAE at least possibly related to the study intervention) it is in the best interest of the participant to discontinue study intervention
- The participant becomes pregnant
- Non-adherence to take the study medication. Non-adherence will be decided on a case-by-case basis depending on the number of missed capsules and the interval between missed doses.
- Aspartate aminotransferase (AST) and/or ALT exceeds 5x the upper limit of normal (ULN) (confirmed by repeat testing)

- AST and/or ALT exceeds 3x the ULN and total bilirubin exceeds 1.5x ULN (confirmed by repeat testing)

If a participant discontinues study intervention for any reason before the end of the double-blind treatment phase, then the early withdrawal assessments should be obtained, and scheduled assessments of study intervention should be continued.

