7.4. Participant Discontinuation/Withdrawal From the Study

A participant will be withdrawn from the study for any of the following reasons:

- If the participant experiences clinically significant worsening of major depression that requires any new intervention based on clinician judgment or participant preference.
- A participant who shows signals of clinically meaningful acute suicidal ideation at any time during the study should be withdrawn from the study and referred for appropriate medical/psychiatric care.

Also, a participant will be automatically withdrawn from the study for any of the following reasons:

- Lost to follow-up
- Withdrawal of consent
- Discontinuation of the study treatment for any reason, including those outlined in Section 7.2, (Discontinuation of Study Intervention)
- Death

Additional participants may be enrolled if a relatively large number of participants discontinue or are withdrawn from the study before the end of the double-blind treatment phase and the number of participants completing the study will be below 132.

These additional participants will receive a new participant ID number and will be assigned to a new randomization code in the IWRS.

Study intervention assigned to the withdrawn participant may not be assigned to another participant.

When a participant withdraws before study completion, the reason for withdrawal is to be documented in the eCRF and in the source document. If the reason for withdrawal from the study is withdrawal of consent, then no additional assessments are allowed.

Withdrawal of Consent

A participant declining to return for scheduled visits does not necessarily constitute withdrawal of consent. Alternate follow-up mechanisms that the participant agreed to when signing the consent form apply as local regulations permit.

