5.3.2.1. Analysis Methods

5.3.2.1.1. Primary Analysis

The primary efficacy analysis will be performed utilizing the hypothetical estimand defined above. The change from baseline in MADRS total score will be compared between the JNJ-55308942 mg once daily group and the placebo group at Week 6 in a mixed-effects model for repeated measures (MMRM), with time, intervention (placebo or JNJ-55308942), BD type (I or II), country, P2RX7 GoF SNP mutation genotype (homozygous or heterozygous), concomitant medication status (no mood stabilizer or antipsychotic, a mood stabilizer alone, an antipsychotic alone, or a combination of a mood stabilizer and an antipsychotic), and time-by-intervention interaction as factors, with baseline MADRS total score as a continuous covariate. Data after treatment discontinuation will be considered missing. The within-subject covariance between visits will be estimated via an unstructured variance-covariance matrix. In case of convergence problems, alternative variance-covariance structures will be attempted in the following order, with the first structure that converges being used in the analysis: heterogeneous Toeplitz, standard Toeplitz, and first order autoregressive. Kenward-Roger approximation will be used to estimate the denominator degrees of freedom. Sandwich estimator will be used to address the potential misspecification of the covariance matrix when a structured covariance matrix is used due to the convergence problem with the unstructured covariance matrix.

The comparison of JNJ-55308942 versus placebo will be performed using the appropriate contrasts directly from the MMRM analysis. A 2-sided 80% confidence interval (CI) for the difference in least squares means will be presented over time. A 1-sided p-value will be calculated at Week 6. Least square means of change from baseline (+/- SE) will be presented graphically over time.

Descriptive statistics of the actual values and the change from baseline to each postbaseline time point will be presented for MADRS total score by intervention group.

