5.3.2.1.2. Sensitivity Analysis

The primary analysis based on MMRM is valid and produces unbiased estimates of the treatment effect if missing data are missing at random (MAR), meaning that the probability of a value being missing, conditional on the observed data in the statistical model, is random and not dependent on the unknown value of missing data point. The MAR assumption cannot be verified vs. missing not at random (MNAR) using observed data. Therefore, a sensitivity analysis using copy-reference multiple imputation will be conducted under the MNAR assumption to evaluate the robustness of efficacy results and the effect of the missing data. In addition, a tipping-point analysis will be conducted if the primary analysis results show a significantly greater improvement in the MADRS

total score at Week 6 in JNJ-55308942 compared to placebo (i.e., 1-sided p-value \leq 0.1 in favor of JNJ-55308942).

The copy reference multiple imputation approach does not assume a sustained benefit of experimental intervention for the efficacy data that is either not used or missing after the intercurrent event and uses an imputation method that is based on the control group distribution and the estimated correlations between time points in the control group. MAR is assumed for intermediate missing data (i.e., missing data between non-missing observations). MNAR is assumed for monotone missing (i.e., missing data after the participant experienced an intercurrent event) in participants in the experimental intervention group, where efficacy scores are assumed as if the participant had always been in the control group. MAR is assumed for missing data in the control group.

This method will employ the following 3 steps:

Step 1 – Multiple imputation

If there are participants with a non-monotone missing data pattern, datasets with only monotone missing data patterns will be created first by imputing the intermediate missing values using the Markov Chain Monte Carlo (MCMC) method, which assumes a multivariate normal distribution over all variables included in the imputation model. This imputation will be done by intervention group. The variables to be used in the imputation are treatment, corresponding baseline values, and values observed at all double-blind visits (Weeks 1, 2, 4, 6). 50 imputations will be performed to create 50 datasets that now have monotone missing (i.e., missing data after the participant experienced an intercurrent event) data pattern.

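### SAP 5.3.2 assumes that any background-therapy change ends study drug; the protocol does not make that automatic, so a probably small number of MADRS scores could stay in the primary MMRM against the SAP's own estimand

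*SAP*

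**What the plan says.** **Estimand.** The table in SAP 5.3.2 has two intercurrent events: discontinuation of study intervention, and change or discontinuation of background therapy. Both get a hypothetical strategy, the second by reference to the first. The SAP adds that change or "discontinuation of background therapy will result in" stopping study intervention. Protocol 9.4.1 names only the first event.

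**Primary data rule.** SAP 5.3.2.1.1: "Data after treatment discontinuation will be considered missing". Background therapy is not mentioned as a trigger.

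**Protocol rules that could stop study drug after a background-therapy change.**
- Section 7.2 gives the cases in which a participant's "study intervention must be discontinued if". None is a background-therapy change. The nearest is a serious protocol violation, which needs discussion with the medical monitor and the monitor's agreement.
- Section 6.7 says "No dose changes are permitted from screening through the end of the study" but attaches no consequence for study drug. After a disallowed medication, "the sponsor and investigator will evaluate whether a participant should be discontinued or remain in the study".
- Section 7.4 withdraws a participant whose worsening depression "requires any new intervention based on clinician judgment or participant preference", or who shows acute suicidal ideation. It also lists automatic withdrawals: loss to follow-up, withdrawn consent, discontinuation of study treatment for any reason, and death.

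**The concern.** The SAP's data rule is enough for both intercurrent events only if the second always leads to the first. That link is stated in the SAP as a fact about conduct, but sites follow the protocol, and the protocol leaves the matter partly to judgement.

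The participants at issue meet all of these conditions: they take a scheduled mood stabilizer or antipsychotic; they change or stop it for a reason such as tolerability, supply or personal choice; they are not taken off study drug as a serious violation or after the section 6.7 review; and they have a later MADRS while still on study drug. Their later scores enter the MMRM as observed. For them the analysis follows a treatment-policy approach, while the SAP asks what would have happened under a hypothetical strategy. At stake is whether the primary estimate answers the question the SAP states, and whether the choice of scores is fixed before unblinding.

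**Working it through.** **1. Does any rule force study drug to stop?**

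| Situation after Day 1 | Protocol rule | Study drug stops automatically? |
|---|---|---|
| Worsening depression needing a new intervention | 7.4 | Yes, through withdrawal |
| Acute suicidal ideation | 7.4 | Withdrawal is called for |
| Disallowed medication taken | 6.7 | No; sponsor and investigator decide |
| Change judged a serious violation | 7.2 | Only with the medical monitor's agreement |
| Dose cut or stop for tolerability, supply or choice | 6.7 bans it | No consequence stated |

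The last row, and the undecided part of the two rows above it, are what the SAP's premise misses.

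**2. Reproduce the plan's sample size.** Inputs from SAP section 3: effect size 0.45 (3.9 points, SD 8.6), 1-sided alpha 0.10, power 90%, dropout 20%.

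n per arm = 2(1.2816 + 1.2816)² / 0.45² = 64.9, rounded up to 65. Then 65 / 0.80 = 81.25, rounded up to 82 per arm, 164 in total. This matches the plan.

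The plan's 132 completers are 66 per arm. SE = 8.6 × √(2/66) = 1.497 and the noncentrality is 3.9 / 1.497 = 2.605. Power by the noncentral t is **0.906**.

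**3. Size if scores are retained.** The documents give no rate of background-therapy change and no effect of one, so every rate and gain here is an assumption.

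Expected difference = 3.9 − (placebo excess × mean MADRS gain), with 66 per arm and SD 8.6:

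| Assumption | Expected difference | Power |
|---|---|---|
| Equal rates and equal gains | 3.90 | 0.906 |
| 1-point placebo excess, gain 3 | 3.9 − 0.01 × 3 = 3.87 | 0.902 |
| 2-point placebo excess, gain 3 | 3.9 − 0.02 × 3 = 3.84 | 0.899 |
| 2-point active excess, gain 3 | 3.9 + 0.02 × 3 = 3.96 | 0.912 |

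Two percent of 66 is 1.3 participants. With no true effect, an apparent benefit of 0.06 raises the 1-sided rejection rate from 0.10 to 0.107.

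To show the range, take deliberately larger imbalances (normal approximation, base power 0.907). With 2% affected on active and 5% on placebo, gains of 3 to 8 points move the difference by 0.03 × 3 = 0.09 to 0.03 × 8 = 0.24, and power is 0.897 to 0.878. With 5% and 10%, the shift is 0.15 to 0.40 and power is 0.889 to 0.855. Rates that high seem unlikely for so narrow a group, but the documents cannot rule them out.

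**4. Cost if the scores are set to missing.** At a difference of 3.9, treating lost Week 6 scores as a plain loss of sample size:
- 2% lost: 66 × 0.98 = 64.7 per arm, power 0.901.
- 5% lost: 66 × 0.95 = 62.7 per arm, power 0.894.

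**The case against.** The strongest reply is that the SAP is coherent on its own terms. If a background-therapy change always ends study drug, the second event is nested in the first and one data rule serves both. A gap then appears only when a site departs from what the SAP expects. The protocol also bans dose changes, reviews disallowed medication and withdraws participants whose depression needs new treatment, and SAP 6.4 identifies major deviations before database lock. All this shrinks the group and supports calling the effect very small. It does not supply the missing rule: the remaining controls are discretionary, and identifying a deviation does not remove a score.

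Three stronger readings are tempting, and the documents do not support them.
- **The copy-reference analysis would use a different cut-off date.** SAP 5.3.2.1.2 speaks of "missing data after the participant experienced an intercurrent event", and with two listed events a reader might infer a cut at the background-therapy change. But that text imputes data already missing or not used, it does not tell anyone to delete observed on-treatment scores, and Protocol 9.4.1 ties the analysis to treatment discontinuation. This is a possible ambiguity at most.
- **Section 7.4 covers only worsening depression and suicidal ideation.** It also lists the automatic withdrawals set out above.
- **SAP 6.2 conceals a changed analysis.** The appendix does omit the second event, but the SAP treats that event as leading to the protocol's single one. This is a minor documentation point.

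**Conclusion.** The point holds as a minor inconsistency. The SAP chooses a hypothetical strategy for background-therapy changes, supports it with a premise that the protocol does not make automatic, and writes a data rule that works only if the premise is true. Whether anyone is affected depends on conduct: someone must change background therapy for a reason outside section 7.4, stay on study drug, and be rated again.

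The plausible size is very small: about one participant per arm in the illustration, with power moving by less than one percentage point. The direction is unknown, and equal rates with equal effects in both arms give no shift. A reader might infer that the primary result is materially biased; nothing in the documents shows that. The sample size is unaffected.

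**What to change.** In SAP 5.3.2.1.1, replace the single trigger with text such as: MADRS data are set to missing after the earlier of (a) discontinuation of study intervention and (b) the first post-Day-1 change in dose or drug, or discontinuation, of the scheduled background mood stabilizer or antipsychotic, whether or not study drug continued.

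Take date (b) from the first new or ended regimen record for that drug in the concomitant-therapy eCRF. State that missed doses, and PRN use permitted by Protocol Appendix 6, do not count. The data already exist, since Protocol 6.7 says: "Recorded information will include a description of the type of therapy, duration of use, dosing regimen, route of administration, and indication". Use the same date in the copy-reference and tipping-point analyses, so that no ambiguity arises. Listing the added event in SAP 6.2 is optional housekeeping.

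**Cost.** One sentence, one definition and one derived date. Slightly more data will be missing, including after a brief change that is later reversed. The power cost (0.901 at 2% lost and 0.894 at 5%, against 0.906) is about the same size as the loss it might prevent, so the reason to act is agreement between estimand and data rule.

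A protocol stopping rule, or a declared treatment-policy strategy for participants who stay on study drug, would also restore consistency. The change above keeps the strategy the SAP has already chosen and needs no protocol amendment.
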